- d. **Office contacts:** The total number and type of office contact between the preoperative visit and the 6-week postoperative visit will be collected via manual chart review. Type of office contact visits include patient-initiated calls, nurse-initiated calls, scheduled office visits, and add-on office visits.
- e. **Canceled, No-show, and late visits:** If patients call to cancel their appointment this will be considered a canceled preoperative visit. Rescheduled appointment will be noted. Patients who arrive to their visit later than 10 minutes will be considered late for each group. If patients do not present for their visit, it will be considered a No-show appointment.
- f. **Calculated value proposition metrics:** The length of visit will be compared between groups. Office schedules will be analyzed and will determine the percentages of new patient visits and preoperative visits. If preoperative visits are replaced with new patient visits over a month, based on institutional data, anticipated new operative cases and projected revenue impact on the health care system will be determined. Costs of video based virtual visit platform will also be calculated.

STATISTICAL CONSIDERATIONS

Statistical Methods

The primary analysis will compare summary scores of preparedness between both study groups. Non-inferiority of virtual visit compared with in-person visit

would be claimed if the upper limit of the one-sided 95% confidence interval for the mean differences of scores between two groups will not exceed the pre-specified margin of 9 points. Descriptive statistics will be calculated to assess level of preparedness for each question. Secondary outcomes, demographics, and other baseline variables will be compared between the two groups using the Chi squared test or Fisher's exact test for categorical data, Student's t test for normally distributed data, and the Wilcoxon rank sum test for ordinal data or continuous data that are not normally distributed.

Sample Size Calculation

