Sample size calculations were based on two-group non-inferiority comparisons of patient preoperative preparedness for surgery using two-sample t-test. The following assumptions were made: the margin of non-inferiority is 9.0 and the data are drawn from populations with standard deviations of 15.0. A sample size of 45 in each arm is needed to achieve a power of 0.8 with $\alpha=0.025$. Considering a 30% drop out rate, we will require 59 patients in each group and a total of 118 participants. The power was calculated by using the PASS 15 (2017, NCSS, LLC. Kaysville, Utah, USA).

STUDY DOCUMENTATION AND MONITORING

Documentation

All study documents included in this protocol that will be presented to subjects will be submitted to the IRB for review. The site will maintain a study binder that will include the following:

- Enrollment log of patients that have consented to be in the study (electronic version)
- Protocol deviation log (electronic version)
- Adverse event log (electronic version)
- Investigator protocol and amendments
- IRB submissions, modifications, and renewals
- Data safety monitoring committee reports
- IRB approved verbal consent forms
- Data collection forms

Study Monitoring

The Principal Investigator will monitor the study and assess the need for amendments as the study progresses. The PI will review the progress of each subject on the study and will apprise the IRB of adverse events or unexpected problems that may influence the IRB's decision to allow the trial to continue, in accordance with the IRB's standard operating procedures and policies. A protocol revision may be necessary for reasons including but not limited to rights, confidentiality of participants, welfare of participants, and thus, an

amendment will be required. Appropriate approvals (i.e., IRB) of the revised protocol must be obtained prior to implementation.

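### The non-inferiority rule works at one-sided alpha 0.05, but the trial was sized at 0.025, so applying the rule as written doubles the design's false non-inferiority rate

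*Combined protocol and SAP*

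**What the plan says.** The decision rule is in Statistical Considerations, Statistical Methods. It rests on "the upper limit of the one-sided 95% confidence interval for the mean differences of scores between two groups". Telemedicine counts as non-inferior when this limit is no greater than 9 points, a margin fixed in advance.

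The Sample Size Calculation, directly after it, concerns the same comparison. It assumes that "the margin of non-inferiority is 9.0" and that "the data are drawn from populations with standard deviations of 15.0", names a two-sample t-test, and concludes: "A sample size of 45 in each arm is needed to achieve a power of 0.8 with $\alpha=0.025". It does not say whether that alpha is one- or two-sided, and it states no assumed true difference. It then allows for 30% drop-out and arrives at 59 per group, 118 in total.

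No other part of the document gives a significance level or a confidence level for the primary comparison.

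**The concern.** Comparing an upper confidence limit with a margin is a one-sided test whose level is one minus the one-sided coverage. A one-sided 95% limit therefore tests at 0.05. The sizing alpha of 0.025 corresponds to a one-sided 97.5% limit, which is the upper limit of a two-sided 95% interval. The two sections describe different tests of the same hypothesis.

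Non-inferiority on preparedness is the primary objective and the only outcome with a pre-specified success criterion. If the rule is followed as written, the chance of accepting a telemedicine visit that is worse by the full margin is twice what the sizing allowed, and the stated power does not describe the test that decides the trial. The study is also unblinded. If the conflict is left open, a result that passes one criterion and fails the other could be called either way after the data are seen.

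**Working it through.** **Inputs from the documents.** Margin 9, SD 15 in each group, power 0.8, alpha 0.025 and a two-sample t-test (Sample Size Calculation); 1:1 allocation (Randomization); one-sided 95% limit (Statistical Methods). **Assumption:** true difference 0, since none is stated.

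**1. Reproduce the stated 45 per arm.** With n per arm, the degrees of freedom are 2n − 2 and the noncentrality is 9 / (15 × √(2/n)). Power is the probability that a noncentral t variable with these parameters exceeds t(1 − α, 2n − 2). At n = 45 the standard error is 15 × √(2/45) = 3.162 and the noncentrality is 9 / 3.162 = 2.846.

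| Reading of alpha | Smallest n per arm with power at least 0.80 | Power at that n |
|---|---|---|
| One-sided 0.025 | 45 | 0.804 (44 gives 0.795) |
| One-sided 0.05 (the written rule) | 36 | 0.809 |
| 0.025 two-sided, i.e. 0.0125 per side | 55 | 0.807 |

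At a true difference of 0, only one-sided 0.025 returns the plan's figure.

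**2. Level of the written rule.** 1 − 0.95 = 0.05, and 0.05 / 0.025 = 2. A simulation at a true deficit of 9 points (SD 15, 45 per arm, 400,000 trials) declared non-inferiority in 5.0% of trials with the one-sided 95% limit and in 2.5% with the one-sided 97.5% limit.

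**3. Largest observed deficit that still passes.** This is 9 − t(1 − α, 88) × 3.162.

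- One-sided 95% limit: 9 − 1.662 × 3.162 = 9 − 5.26 = 3.74 points.
- One-sided 97.5% limit: 9 − 1.987 × 3.162 = 9 − 6.28 = 2.72 points.

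An observed deficit between 2.72 and 3.74 points passes Statistical Methods and fails at the sizing alpha. If all 59 per group were evaluable, the limits would be 4.42 and 3.53.

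**4. Power at a true difference of 0.**

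| Evaluable per arm | One-sided 0.05 (as written) | One-sided 0.025 (sizing alpha) |
|---|---|---|
| 45 | 0.881 | 0.804 |
| 41 (59 × 0.70 = 41.3) | 0.853 | 0.765 |

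**5. Dependence on the SD.** The 5% against 2.5% contrast does not depend on the SD, but the limits in points do. If the SD were 7.5 (an assumption, half the planned value), the limits at 45 per arm would be 6.37 and 5.86, a gap of about 0.5 point instead of about 1.0.

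**The case against.** - **Wording slip.** The author may have meant the upper limit of a two-sided 95% interval. The true error rate would then be 2.5% and nothing would double. This is quite likely the origin of the conflict, but an analyst following the text would compute a one-sided 95% limit, so the sentence still has to change.
- **The sizing may simply be conservative.** Alpha in a sample size section is an input, and the success criterion is in Statistical Methods. A sponsor may choose one-sided 0.05, and the documents cite no standard against it. That would also be consistent, but only if the sample size section were restated and the looser level justified. The plan does neither.
- **45 per arm is not unique to one-sided 0.025.** This is true if the true difference is left free: with a true deficit of about 1.05 points, one-sided 0.05 also gives 45 per arm at power 0.80. The mismatch does not rest on that inference, however, because 0.025 is printed in the plan.
- **The stricter rule is not free in power.** This stands. At the planned 30% drop-out, 59 per group leaves about 41, and power at one-sided 0.025 is 0.765. The cause is a separate matter: 59 is 45 × 1.3 = 58.5 rounded up, whereas 45 / 0.70 = 64.3 calls for 65. The looser rule hides that shortfall, because its power at 41 per arm is 0.853.

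**Conclusion.** The concern holds and should be settled before analysis. The written criterion tests at one-sided 0.05 while the trial was designed at 0.025. Followed literally, it doubles the false non-inferiority rate at a true deficit of 9 points, from 2.5% to 5.0%, and raises the largest passing deficit by about one point (2.72 to 3.74). The doubling follows from the confidence level alone. The figures in points assume SD 15 and 45 evaluable per arm, and the power figures also assume a true difference of 0. The mismatch does not leave the trial underpowered under the written rule; the harm is a success criterion looser than the one the sample size was built on.

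**What to change.** Replace the sentence in Statistical Methods with a rule of this kind: non-inferiority is claimed if the upper limit of the two-sided 95% confidence interval (equivalently, the one-sided 97.5% limit) for the mean difference, telemedicine minus in-office, does not exceed 9 points. Stating the direction of subtraction is worthwhile: each preparedness item runs from 1 (strongly agree) to 6 (strongly disagree), so a higher sum means less prepared and the upper limit is the relevant one. In the Sample Size Calculation, state that alpha 0.025 is one-sided and give the assumed true difference.

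This costs one sentence plus that clarification, and a stricter criterion. The 45 evaluable per arm does not change. Holding 80% power after 30% drop-out needs 65 enrolled per group rather than 59, or drop-out below the planned rate; that comes from the drop-out inflation, not from this correction.

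If the sponsor prefers one-sided 0.05, the alternative is to keep the rule, restate alpha and power in the sample size section (0.881 at 45 per arm, 0.853 at 41) and justify the looser level. Either choice should be recorded before outcome data are examined.

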An Atrium Health biostatistician will generate a randomization sequence using SAS Enterprise Guide 6.1. A permuted block randomization scheme will be used to assign patients in a 1:1 ratio to Telemedicine visit or In-office visit.

The study will not be blinded.

DATA COLLECTION AND MANAGEMENT

Data Collection Schedule

Case report forms will be developed by the investigators. Data will be collected prospectively per the schedule in Table 1. All study data will be recorded by research staff and securely maintained at the Mercy study site. The data flow will consist of paper data collection for eligibility assessment, baseline data, randomization, intervention group, primary and secondary outcomes, and protocol deviations.

Data will be entered by study staff into REDCap database that will be stored on a secure server at Atrium Health. Web-based survey responses will be linked to REDCap for automatic entry following participant submission of surveys. REDCap (Research Electronic Data Capture) is a secure, web-based application designed to support data capture for research studies providing: 1) an intuitive interface for validated data entry; 2) audit trails for tracking data manipulation and export procedures; 3) automated export procedures for seamless data downloads to common statistical packages; and 4) procedures for importing data from external sources (13).

Each patient will have a unique identification number to which only the principal and sub-investigators will have access. The data collection spreadsheet will not contain any patient identifiers and will be password protected. The master list that links the patients and their study information will be stored separately on a password protected hard drive. A back up copy of the file will be stored on a password protected hospital network drive. All hard copies of study data will be stored in a locked cabinet in the office of the research nurse, which will also be locked.

Table 1. Data Collection Schedule

	Prior to Preoperative visit	Preoperative visit	Period between Preop visit and surgery	Surgery	2 week postop visit	6 week postop visit
Informed consent	X					
Randomization	X					
Travel distance	X					
Internet Access/Usage	X	X				
Other Demographics*	X	X				
Patient Preparedness		X				
Patient Satisfaction					X	
Office visits		X	X		X	X
Cost metrics						X

*Other demographic data includes: Age, Race, Education level, Health literacy score, and number of prior surgeries.

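### At the plan's own 30% dropout, 59 per arm leaves about 41 evaluable, not the 45 it requires, and power at one-sided alpha 0.025 is about 0.77 rather than 0.80

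*Combined protocol and SAP*

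**What the plan says.** The Sample Size Calculation section bases the trial on "two-group non-inferiority comparisons of patient preoperative preparedness for surgery using two-sample t-test". It assumes that "the margin of non-inferiority is 9.0" and that "the data are drawn from populations with standard deviations of 15.0". From these it concludes: "A sample size of 45 in each arm is needed to achieve a power of 0.8", with alpha set at 0.025. The next sentence gives the enrolment target: "Considering a 30% drop out rate, we will require 59 patients in each group and a total of 118 participants". The inflation formula is not printed, and neither the sidedness of alpha nor the assumed true difference is stated.

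Two other places bear on the point. The Randomization section fixes equal allocation: "A permuted block randomization scheme will be used to assign patients in a 1:1 ratio". Statistical Methods bases the non-inferiority decision on the "upper limit of the one-sided 95% confidence interval for the mean differences of scores between two groups", which corresponds to a one-sided alpha of 0.05, not 0.025.

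**The concern.** A dropout allowance should ensure that the required evaluable number remains after the stated fraction is lost. Here it does not: removing 30% from 59 gives fewer than 45, so the allowance fails at the very rate it is meant to cover.

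At stake is the power of the primary comparison. In a non-inferiority trial, lower power raises the chance of failing to show non-inferiority when telemedicine really is no worse. A reader of the plan would believe that 118 participants protect 80% power against 30% loss; on the plan's own inputs they do not.

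**Working it through.** **Inputs.** From Sample Size Calculation: margin 9.0, SD 15.0 in each arm, alpha 0.025, power 0.80, 45 evaluable per arm, 30% dropout, 59 enrolled per arm, 118 in total. From Randomization: 1:1 allocation. Assumed here because it is not stated: a true difference of 0.

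**Step 1. Reproduce the 45.** For a two-sample t-test with n per arm, the degrees of freedom are 2n − 2 and the non-centrality is margin / (SD × √(2/n)). Power is the probability that a non-central t variable with that non-centrality exceeds the one-sided critical value.

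- n = 45: non-centrality 9 / (15 × √(2/45)) = 2.846; critical value 1.987 on 88 df; power 0.804.
- n = 44: power 0.795.

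So 45 is the smallest n reaching 0.80 at one-sided alpha 0.025. The other readings do not give 45: one-sided 0.05 needs 36, and 0.025 read as two-sided needs 55. The stated 45 therefore rests on one-sided 0.025 and a true difference of 0.

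**Step 2. Reproduce the 59.**

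- 45 × 1.30 = 58.5, rounded up to 59. This matches.
- 45 / (1 − 0.30) = 64.3, rounded up to 65. This does not match.

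**Step 3. What 59 delivers at 30% dropout.**

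- Evaluable per arm: 59 × 0.70 = 41.3, about 41, which is 4 short of 45.
- Largest dropout that still leaves 45: 1 − 45/59 = 23.7%, or 14 losses per arm.
- Enrolment needed for 45 evaluable at 30%: 65 per arm (65 × 0.70 = 45.5), 130 in total, which is 130 − 118 = 12 more.

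**Step 4. Power with 41 evaluable per arm.** Non-centrality is 9 / (15 × √(2/41)) = 2.717 on 80 df.

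| Evaluable per arm | One-sided alpha 0.025 | One-sided alpha 0.05 |
|---|---|---|
| 45 | 0.804 | 0.881 |
| 41 | 0.765 | 0.853 |

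Letting the number of dropouts vary at random around 30% of 59 per arm gives an average power of 0.766 at 0.025, essentially the same. The normal approximation gives 0.775 for 41 per arm, also short of 0.80.

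**Step 5. The same calculation on the other alpha.** If one-sided 0.05 governs, 36 evaluable per arm suffice (power 0.809), and 36 / 0.70 = 51.4, so 52 enrolled per arm. The stated 59 does not follow from that basis either.

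**The case against.** The strongest objection is that the power shortfall is conditional. The only decision rule in Statistical Methods is a one-sided 95% interval. Under it, 41 evaluable per arm gives 0.853, and 59 enrolled exceeds the 52 needed. If that rule governs, the trial loses nothing against its 80% target. This stands as a limit on the consequence. It does not repair the text, because the plan ties its 45 and its 0.8 to alpha 0.025.

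Three lesser objections also have some force.

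- **The multiplication by 1.3 is inferred.** No formula is printed. The numerical match makes it very likely, but the inconsistency does not depend on it: 59 × 0.70 is below 45 however 59 was reached.
- **The effect is small.** It is about 4 points of power. With 41 per arm, an SD of about 14.3 instead of 15.0 would restore 0.80, and the SD is given without a source. The gap lies within the likely uncertainty of the planning inputs.
- **Actual loss may be below 30%.** In-office participants are asked to complete the survey before leaving. Telemedicine participants get an emailed link and an email reminder, then a phone reminder or collection on the day of surgery. Those who switch to an in-office visit are analysed by intention to treat. A real shortfall is therefore less likely, but 30% is the plan's own figure; if a lower rate is expected, the plan should state it.

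**Conclusion.** The point holds. The requirement of 45 evaluable per arm, the 30% dropout rate and the enrolment of 59 per arm cannot all stand. At 30% dropout the plan falls 4 evaluable patients per arm short of its own requirement, and power drops from 0.804 to 0.765 at one-sided alpha 0.025. The arithmetic contradiction needs no assumption beyond the plan's stated figures. The power figures rest on margin 9, SD 15, a true difference of 0 (needed to reproduce 45) and one-sided 0.025 as the governing level; at one-sided 0.05, power stays above 0.80. The loss is modest, but the sample size statement is wrong as written and should be corrected.

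**What to change.** First decide which one-sided alpha governs and state it identically in Statistical Methods and Sample Size Calculation. Then correct the dropout sentence.

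**If 0.025 is kept**, retain 118 and state one of the following:

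- 59 per arm retains 45 evaluable provided dropout is at most 23%; or
- at 30% dropout about 41 per arm are evaluable, with power about 0.77 at one-sided alpha 0.025.

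Either is a change of one sentence and needs no extra patients; the cost is a slightly less favourable claim. To keep both the 30% allowance and 80% power, the sponsor would have to enrol 65 per arm, 130 in total, which costs 12 more participants.

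**If 0.05 is kept**, replace the evaluable requirement of 45 with 36 per arm. The stated enrolment then exceeds the 52 per arm needed at 30% dropout, and 118 needs no power caveat.

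In either case, print the inflation as evaluable number / (1 − dropout rate), and state the sidedness of alpha and the assumed true difference.

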If you want to know more about this study, please call [name] at [contact] or email at [contact]

Survey Instructions

Answer each question by clicking the box to the left of your answer. When you have selected your desired response, please click “Next”.

- 1 Yes
2 No

1. I know about the *Alternatives* to the planned surgery.

- 1 Strongly agree
- 2 Agree
- 3 Somewhat agree
- 4 Somewhat disagree
- 5 Disagree
- 6 Strongly disagree

2. I understand the *Purpose* of the planned surgery (what this surgery can accomplish).

- 1 Strongly agree
- 2 Agree
- 3 Somewhat agree
- 4 Somewhat disagree
- 5 Disagree
- 6 Strongly disagree

3. I understand the *Benefits* of the planned surgery (how this surgery should help me).

- 1 Strongly agree
- 2 Agree
- 3 Somewhat agree
- 4 Somewhat disagree
- 5 Disagree
- 6 Strongly disagree

4. I understand the *Risks* of the planned surgery (what are the chances of something not going the way my doctor and I want it to go?).

- 1 Strongly agree
- 2 Agree
- 3 Somewhat agree
- 4 Somewhat disagree
- 5 Disagree
- 6 Strongly disagree

5. I understand the *Complications* of the planned surgery (what problems can come from this surgery?).

- 1 Strongly agree
- 2 Agree
- 3 Somewhat agree
- 4 Somewhat disagree
- 5 Disagree
- 6 Strongly disagree

6. I feel prepared about *what to expect after surgery while I am in the hospital.*

- 1 Strongly agree
- 2 Agree
- 3 Somewhat agree
- 4 Somewhat disagree
- 5 Disagree
- 6 Strongly disagree

7. I feel prepared about *what to expect after surgery when I am at home.*

- 1 Strongly agree
- 2 Agree
- 3 Somewhat agree
- 4 Somewhat disagree
- 5 Disagree
- 6 Strongly disagree

8. I feel prepared to cope with a *catheter* after the surgery while I am at the hospital.

- 1 Strongly agree
- 2 Agree
- 3 Somewhat agree
- 4 Somewhat disagree
- 5 Disagree
- 6 Strongly disagree

9. I feel prepared to cope with a *catheter* after the surgery when I am at home.

- 1 Strongly agree
- 2 Agree
- 3 Somewhat agree
- 4 Somewhat disagree
- 5 Disagree
- 6 Strongly disagree

10. My doctors and nurses have spent enough time preparing me for my upcoming surgery.

- 1 Strongly agree
- 2 Agree
- 3 Somewhat agree
- 4 Somewhat disagree
- 5 Disagree
- 6 Strongly disagree

11. Overall, I feel prepared for my upcoming surgery.

- 1 Strongly agree
- 2 Agree
- 3 Somewhat agree
- 4 Somewhat disagree
- 5 Disagree
- 6 Strongly disagree

Think about the type of preoperative visit you had prior to your surgery.

12. Please select the type of visit you had:

- ¹ In-office visit
² Virtual visit

13. How satisfied are you with the visit that you had before your surgery?

- ¹ Very satisfied
² Satisfied
³ Neither satisfied or dissatisfied
⁴ Not satisfied
⁵ Very dissatisfied

14. How would you rate the level of convenience of the visit (virtual or in-person)?

- ¹ Very convenient
² Convenient
³ Neither convenient or inconvenient
⁴ Not convenient
⁵ Very inconvenient

15. If you need to have surgery in the future, would you like to have this type of visit again?

- ¹ Yes
² No
³ Not sure

16. Would you recommend the type of visit you had to a friend?

- ¹ Yes
² No
³ Not sure

17. If in the future our clinic offered the option to have a preoperative visit using virtual visit technology or an in-person clinic visit, which would you prefer?

- 1 Virtual visit
- 2 In-person clinic visit
- 3 No preference

18. What types of technology have you used in the past to access health care services or personal health information? Select all that apply:

- 1 Video conferencing (virtual visit)
- 2 Email
- 3 Text messaging
- 4 Patient Portal (e.g. My Carolinas)
- 5 Mobile health (accessing health services or personal health data via mobile devices)
- 6 Other: _____
- 7 None

The following questions will help us determine comfort level with health information.

19. How often do you have someone (like a family member, friend, hospital/clinic worker, or caregiver) help you read hospital materials?

- 1 None of the time
- 2 A little of the time
- 3 Some of the time
- 4 Most of the time
- 5 All of the time

20. How often do you have problems learning about your medical condition because of difficulty understanding written information?

- 1 None of the time
- 2 A little of the time
- 3 Some of the time
- 4 Most of the time
- 5 All of the time

21. How confident are you filling out forms by yourself?

- 1 Extremely
- 2 Quite a bit
- 3 Somewhat
- 4 A little bit
- 5 Not at all

Figure 3. Postoperative visit survey

Your Privacy is Protected. All information that would let someone identify you or your family will be kept private. The Women’s Center for Pelvic Health will not share your personal information with anyone. Your responses to this survey are also completely **confidential**.

Your Participation is Voluntary. You may choose to answer this survey or not. If you choose not to, this will not affect the health care you get.

What To Do When You’re Done. Once you complete the survey, please return the survey to your nurse.

If you want to know more about this study, please call [name] at [contact] or email at [contact]

Survey Instructions

Answer each question by clicking the box to the left of your answer. When you have selected your desired response, please click “Next”.

- 1 Yes
2 No

1. Before your surgery, how many visits did you have with your surgeon and their assistant surgeons?

- None
- 1 visit
- 2 visits
- 3 visits
- 4 to 6 visits
- 7 or more visits

2. A health provider could be a doctor, nurse, or anyone else you would see for health care. Before your surgery, did anyone in your surgeon's office give you all the information you needed about your surgery?

- Yes, definitely
- Yes, somewhat
- No

3. Before your surgery, did anyone in your surgeon's office give you easy to understand instructions about getting ready for your surgery?

- Yes, definitely
- Yes, somewhat
- No

4. During your visits before your surgery, did your surgeon or their assistant surgeon tell you there was more than one way to treat your condition?

- ¹ Yes
² No

5. During your visits before your surgery, did your surgeon or their assistant surgeon ask which way to treat your condition you thought was best for you?

- ¹ Yes
² No

6. During your visits before your surgery, did your surgeon or their assistant surgeon talk with you about the reasons you might want to have the surgery?

- ¹ Not at all
² A little
³ Some
⁴ A lot

7. During your visits before your surgery, did your surgeon or their assistant surgeon talk with you about the reasons you might not want to have the surgery?

- ¹ Not at all
² A little
³ Some
⁴ A lot

8. During the visits before your surgery, did your surgeon or their assistant surgeon listen carefully to you?

- ¹ Yes, definitely
² Yes, somewhat
³ No

9. During your visits before your surgery, did your surgeon or their assistant surgeon spend enough time with you?

- ¹ Yes, definitely
- ² Yes, somewhat
- ³ No

10. During your visits before your surgery, did your surgeon or their assistant surgeon encourage you to ask questions?

- ¹ Yes, definitely
- ² Yes, somewhat
- ³ No

11. During your visits before your surgery, did your surgeon or their assistant surgeon show respect for what you had to say?

- ¹ Yes, definitely
- ² Yes, somewhat
- ³ No

12. During your visits before your surgery, did anyone in your surgeon's office use pictures, drawings, models, or videos to help explain things to you?

- ¹ Yes
- ² No

13. Did these pictures, drawings, models, or videos help you better understand your condition and its treatments?

- ¹ Yes, definitely
- ² Yes, somewhat
- ³ No, these were not helpful.
- ⁴ No, my surgeon's office did not use these.

Think about the type of preoperative visit you had prior to your surgery.

14. Please select the type of visit you had:

- ¹ In-office visit
² Virtual visit

15. How satisfied are you with the visit that you had before your surgery?

- ¹ Very satisfied
² Satisfied
³ Neither satisfied or dissatisfied
⁴ Not satisfied
⁵ Very dissatisfied

16. How would you rate the level of convenience of the visit (virtual or in-person)?

- ¹ Very convenient
² Convenient
³ Neither convenient or inconvenient
⁴ Not convenient
⁵ Very inconvenient

17. If you need to have surgery in the future, would you like to have this type of visit again?

- ¹ Yes
² No
³ Not sure

18. Would you recommend the type of visit you had to a friend?

- ¹ Yes
² No
³ Not sure

19. If in the future our clinic offered the option to have a preoperative visit using virtual visit technology or an in-person clinic visit, which would you prefer?

- 1 Virtual visit
- 2 In-person clinic visit
- 3 No preference
